Protocol version 2

Date: 28 Mar 2022

TITLE: Effects of tDCS on Post-stroke Fatigue and Inflammation

IRB Protocol Number: 118687

PI: [name]
Research Associate
Division of Physical Therapy
Department of Rehabilitation Sciences
College of Health Professions
Medical University of South Carolina

BACKGROUND / SIGNIFICANCE

Stroke is the most common cause of long-term disability in the United States. Fatigue is a common sequela of stroke and many other neurological conditions. There is no universally accepted definition of fatigue or post-stroke fatigue. However, it is generally accepted that fatigue can be dichotomized into fatigability, an objectively measured decline in physical or cognitive performance, and the perception of fatigue (Kluger et al. 2014, Enoka et al. 2021). The perception of fatigue is defined as a feeling of weariness/tiredness or mismatch between an individual's perceived and actual effort that negatively affects their ability to perform physical, cognitive, and social activities that is not alleviated with rest. A model of post-stroke fatigue (PSF) is presented Figure 1 (adapted from Enoka et al. 2021). Even though the negative impacts of fatigue on quality of life and social/physical activity participation post-stroke are well known, there are currently no evidence-based treatments for post-stroke fatigue (PSF, Hinkle et al. 2017). The development of effective treatments is lacking in part due to the complex and poorly understood pathophysiology of PSF. The recent NIH-sponsored workshop "Beyond the Symptom: The Biology of Fatigue" highlighted this fact and called for more extensive research into the mechanisms and treatments of fatigue. While specific mechanisms of individual patients are unknown, altered immune function, i.e., inflammation (Wen et al. 2018), changes in tissue metabolism (Roelcke et al. 1997), disruptions in interoception (Gonzalez Campo et al. 2020), and altered neural network function (Høgestøl et al. 2019) have been implicated across neurological conditions.

Specific to stroke, a meta-analysis reported the prevalence of PSF is 50% (Cumming et al. 2016). A recent survey of stroke survivors listed PSF treatments as the second most prioritized area of need behind walking/mobility (Rudberg et al. 2020). When dichotomizing the survey's respondents by age, younger stroke survivors reported PSF treatment as their number one priority area. The latest scientific statement from the American Heart Association spotlights the inflammatory and altered cortical excitability components of PSF (Hinkle et al. 2017). Transcranial direct current stimulation (tDCS) has been reported to affect inflammation and cortical excitability. A recent small tDCS study reported beneficial effects on PSF but did not investigate conclusive mechanisms of action or response (De Doncker et al. 2021). Our contribution to this line of inquiry will be to further test the clinical effects of tDCS on PSF and measure markers of inflammation within the central nervous system and peripheral circulation. We expect to identify a link between inflammation and PSF which will significantly contribute to a better understanding of the pathophysiology of fatigue and establish neuromodulatory therapies, such as tDCS, as effective treatments for PSF.

INNOVATION

The effect of tDCS on non-neuronal cell populations has received little attention to date. Basic and pre-clinical research shows small electrical currents, such as the ones used by tDCS, can induce cell differentiation and migration (reviewed by Pelletier and Cicchetti 2015) and alter immune cell function leading to reduced inflammatory markers (Rabenstein et al. 2019, Zhang et al. 2021). Studies in humans have shown reduced circulating inflammatory cytokines after five days of tDCS (Osteoarthritis, Suchting et al. 2020). Stroke is known to induce neuroinflammatory/immune responses and certain inflammatory/immune markers remain elevated one year post incident (Beamer et al. 1998). Inflammation has also been shown to interfere with rehabilitation and could possibly contribute to post-stroke depression (reviewed by Fang et al. 2019). There are reports of anodal-tDCS (a-tDCS) leading to reduced fatigue severity post-stroke and in MS. However, these reports have relatively

[figure not shown]

Figure 1: A model defining post-stroke fatigue, adapted from a schema of fatigue in multiple sclerosis by Enoka et al. (2021). An individual's current State fatigue is measured on a 0-10 Visual Analogue Scale (f-VAS) representing their perception of fatigue at the moment of assessment. The most common method to assess and diagnose clinical fatigue is the Fatigue Severity Scale (FSS), which is thought to measure the effect of fatigue on an individual's perceived ability to perform tasks.

small samples and did not identify/investigate possible mechanisms of effects/response. This pilot project is innovative because it uses a multimodal approach to investigate the effects of tDCS on measures of cortical excitability and effects on inflammation, which likely play roles in the development and severity of PSF. Future investigations derived from this line of inquiry have the opportunity to greatly enhance our understanding of the pathophysiological mechanisms of PSF, identify effective neuromodulatory therapies, and pinpoint a phenotypic response criterion for future clinical trials, i.e. individuals with PSF due to inflammation. An additional innovation is using MR spectroscopy to measure markers of nervous system inflammation. MR spectroscopy is a well-established tool. However, its use in assessing metabolite changes with neuromodulatory therapies is not common due to most tDCS research focusing on cortical excitability and/or neural network function. Using MR spectroscopy will allow us to quantify in-vivo changes in metabolites and inflammatory markers in individuals with PSF in response to tDCS.

APPROACH

Recruitment and Consent

Prospective participants will be recruited from our bioinformatics enabled post-stroke recruitment database which is maintained by the NIH Center of Biomedical Research Excellence in Stroke Recovery at the Medical University of South Carolina. This database, RESTORE, contains over 1200 individuals post-stroke who have consented to be contacted for research purposes. Veterans from our VA-approved recruitment data have agreed to have their contact information placed in RESTORE and their veteran-status is highlighted. Prospective participants more than six months post-stroke will be identified by their response to question 4 of the Personal Health Questionnaire Depression Scale (PHQ-8) stored in their database record. A response of 2 or 3 indicates "Feeling tired or having little energy" on at least half the days over the last 2 weeks. Veterans who participated in the recently completed VA RR&D sponsored study "Fatigue and Mobility in Stroke: a Biomechanical and Neurophysiological Investigation" (IK1 RX0003126, CDA-1, PI: [name]) will be preferentially contacted and recruited to participate in this project. Initial contact will be made with prospective participants via telephone. The project basics will be explained and interested individuals will be invited to our research laboratory for final eligibility screening and consent. *Full inclusion and exclusion criteria are listed in the "Protection for Human Subjects" section.* Once consented, participants will complete a set of questionnaires to assess levels of state and trait fatigue, depression, anxiety, and pain. State fatigue is defined as a participant's instantaneous perception of fatigue and is measured on a 0-10 visual analogue scale (f-VAS) with 0 signifying no feelings of fatigue and 10 representing the most fatigued an individuals could imagine. Trait fatigue refers to an individual's perception of fatigability, i.e. how fatigue affects their ability to perform activities of daily living and participate in social and physical activities. The most common instrument used to measure trait fatigue is the Fatigue Severity Scale (FSS, Krupp et al. 1997). The FSS is a nine-question, scored on a 1-7 likert scale, self-reported questionnaire assessing the impact of fatigue on a variety of activites over the last seven days. An average score of 4 on the FSS signifies clinically relevant fatigue (total FSS score ≥ 36). Additional clinical tests and questionnaires will be performed to measure physical disability (gait speed), balance, and quality of life. Women of childbearing potential will perform a urinalysis to determine pregnancy status. Pregnant women will be excluded due to unknown effects of tDCS on fetal development and mother's milk. The

[figure not shown]

Figure 2: Research protocol timeline. Three additional followup phone-calls to assess fatigue will be performed 1, 2, and 4 weeks post the participants' last tDCS treatment.

full list of questionnaires and clinical measures is presented in Table 1. *The primary outcome for this study is trait fatigue measured by the FSS.*

Study Design and a-tDCS Treatment

This pilot proposal is a randomized longitudinal single-blind sham-controlled intervention. Individuals with PSF will be randomly assigned to the sham or a-tDCS treatment group. Before and after five consecutive days of a-tDCS applied bilaterally over the left and right lower extremity motor cortex, PSF and nervous system and peripheral inflammation will be measured, similar to De Doncker et al. (2021). The tDCS treatment will consist of twenty minutes of 4 mA a-tDCS delivered via two carbon rubber electrodes placed inside sponge pads (1x1 tDCS, Soterix, USA). The current will be ramped up 4 mA over 30 seconds. Each electrode has a surface area of 70 cm², resulting in a current density of 0.06 mA/cm² and a charge density of 1.1 C/cm², which are within current safety guidelines (Bikson et al. 2016). The anode electrode will be centered on the interhemispheric fissure and the central sulcus. This area was chosen due to its previous use in fatigue studies using neuromodulation (multiple sclerosis, Ferrucci et al. 2014; fibromyalgia, Altas et al. 2019; Stroke, De Doncker et al. 2021). The motor cortex is being used more often in neuromodulation studies due to its structural and functional connectivity to cortical and subcortical networks/nodes, e.g. basal ganglia, cingulate cortex. The cathodal electrode will be placed on the nonparetic shoulder. Modeling of cephalic and extracephalic tDCS montages indicates that extracephalic placement of the cathode leads to deeper current flow in the somatosensory cortex (Noetscher et al. 2014). The sham tDCS procedure will be performed in the same manner as active a-tDCS, however, the current will be ramped up and down over 30 seconds (Fridricksson et al. 2018). Figure 2 displays the protocol timeline. Days 2-6 will be consecutive, no more than 36 hours will be allowed between treatment visits. If more than 36 hours elapses the participant will be withdrawn from the study. The measurement of state fatigue, via f-VAS, will be performed before and after each tDCS treatment visit. Follow-up assessments of state and trait fatigue will be performed via phone at one (Follow-up 1), two (Follow-up 2), and four weeks post-treatment (Follow-up 3). The primary study outcome will be the comparison of the FSS scores obtain at baseline (Visit 1) and one week post-tDCS (Follow-up 1).

Neuroimaging

Anatomical and spectroscopic images (T1, T2, ¹H-MRS) will be acquired using the Center for Biomedical Imaging at MUSC's standard imaging protocols. The T1 and T2 images will be used for the computation of stroke lesion locations and volumes. The T1 images will also be used to guide the corticomotor response (CMR) testing listed below. We will use Single-voxel MEGhcher-GArwood Point RESolved Spectroscopy (MEGA-PRESS) ¹H-MRS to assess central nervous system inflammation. Voxels will be placed in the basal ganglia and insular cortex in both hemispheres. Basal ganglia voxels will be placed with the anterior border abutting the anterior portion of the lentiform nucleus and as medial as possible to avoid the ventricles (Pretzsch et al. 2019). The basal ganglia have been previously implicated in fatigue post-stroke (Tang et al. 2010) and in multiple sclerosis (Roelcke et al. 1997, Tellez et al. 2008). The insular cortex is a prominent brain region involved in interoception. Interoception is the sensing, integrating, interpreting and regulating self-signals and has been theorized to contribute to fatigue (Stephan et al. 2016, Enoka et al. 2021) and implicated in fatigue in multiple sclerosis (Gonzalez Campo et al. 2020). Levels of Myo-inositol (MI), total creatine (tCr), and choline (CHO) and their ratios to N-acetylaspartate (NAA) will be quantified as markers of inflammation (reviewed by Chang et al. 2015). Spectroscopy data will be analyzed using the freely available LCModel software as in our previous works (Moss et al. 2018, 2019). Pre and post tDCS intervention spectroscopy values will be compared to determine changes in inflammatory markers associated with the intervention. The measurement of state fatigue will be performed before and after each imaging session.

Blood collection and analysis

Before and after five days of tDCS treatment, participants will provide a blood sample for the measurement of pro-inflammatory cytokines. These cytokines include interleukin- (IL) 1, 6, and 10, tumor necrosis factor (TNF) α , and c-reactive protein. Whole blood will be collected in EDTA-treated tubes and separated into plasma, immune cells (buffy coat), and red blood cells. Separated samples will be frozen and stored until the end of the study. Once all samples are collected they will undergo Simple Plex™ microfluidic ELLA platform immunoassay (ProteinSimple, USA) analysis for listed cytokines (Leligdowicz et al. 2017, Burke et al. 2021). State fatigue will

be measured just prior to blood collection. Blood will be collected at the South Carolina Clinical and Translational Research Institute (SCTR), located on the MUSC/VA shared campus, by skilled medical staff.

Corticomotor Response (CMR)

The CMR of the paretic and non-paretic tibialis anterior will be measured immediately before and after the tDCS intervention using neuronavigated single- and paired-pulse TMS (Brainsight, Rogue Research, CAN) to identify if changes in the CMR are associated with changes in PSF fatigue severity. Preliminary, unpublished, data from our lab identified a link between asymmetries in intracortical facilitation (ICF) between the lesioned and non-lesioned hemispheres and PSF severity. Single-pulse TMS will be used to measure resting motor threshold (rMT) and motor evoked potential amplitude (MEP_{amp}) and latency (MEP_{lat}). Paired-pulse TMS will be used to assess glutamatergic activity signified by intracortical facilitation (ICF). Prior to the participants' first interventional visit, a 7x5 grid will be placed over the participants' acquired 3D T1 image. The middle grid point will be centered on the intersection between the interhemispheric fissure and central sulcus. Surface electromyography (sEMG) electrodes will be placed over the left and right TA. The CMR assessment will begin with the identification of the stimulator powers required to elicit a consistent response in the paretic and non-paretic TA. Once these power levels have been determined a single TMS pulse at each of the identified power outputs will be delivered over the respective grid points. The gridpoint resulting in the largest MEP_{amp} for each muscle will be determined to be the "hotspot" (Kindred et al. 2021). Resting MT will be assessed using simple adaptive parameter estimation by sequential testing (PEST, Borckhardt et al. 2006) measured at the respective hotspots. Next, 20 single TMS pulses will be delivered at 120% rMT for measurement of MEP_{amp} and MEP_{lat}. Paired-pulse TMS will be applied to measure ICF with the conditioning pulse delivered at 80% rMT followed by the conditioned pulse at 120% rMT, using an interstimulus interval of 10 ms,. The recorded sEMG signals will be analyzed using the standard laboratory operating procedures (Kindred et al. 2019, 2020). Neurophysiological variables before and after the tDCS interventional will be compared to determine if changes in PSF severity are associated with changes in the CMR. State fatigue will be measured pre and post the CMR assessment.

Table 1: Clinical Outcome Measures

Domain	Instrument
Fatigue (State)	Visual Analogue Scale
Fatigue (Trait)	* Fatigue Severity Scale (FSS) (Krupp et al. 1989) Modified Fatigue Impact Scale (mFIS) (Fisk et al. 1994) Fatigue Assessment Scale (FAS) (Michielsen et al. 2003)
Anxiety	Hospital Anxiety and Depression Scale (Zigmond and Snaith 1983)
Depression	Patient Health Questionnaire 9 (PHQ-9) (Spitzer and Williams 1999)
Pain	Defense and Veterans Pain Rating Scale (DVPRS) (Polomano et al. 2016)
Physical Function / Mobility	10 m walk over GAITRite (Kindred et al. 2019)
Community Participation / Quality of Life	Standard Form 36 (Anderson et al. 1996)

* Primary outcome measure for Aim 1

Statistical Analysis

Aim 1 Hypothesis: Five days of a-tDCS applied to the lower extremity motor cortex will result in a reduction of PSF severity in individuals with chronic stroke. A two-factor, between-subjects factor of GROUP (active a-tDCS, sham) and within-subjects factor of TIMEPOINT (pre, post), mixed model ANOVA will be used to test this hypothesis. The primary outcome variable for this analysis is the FSS scores. We will also calculate measures of effect size to power future studies.

Aim 2 Hypothesis: Five days of a-tDCS applied to the lower extremity motor cortex will result in a reduction of inflammatory markers within the central nervous system and the peripheral blood. Pre- and post-intervention markers of inflammation will be compared using a mixed model, two-factor ((between-subjects factor of GROUP (active a-tDCS, sham) and within-subjects factor of TIMEPOINT (pre, post)), ANOVA. Each outcome measure (MI, tCR, IL-1, TNF- α , etc) will be tested independently.

Additional Analyses: Examine the possible relationship between PSF severity and inflammatory markers. This relationship may provide mechanistic insight into the effect of tDCS on PSF and allow us to possibly predict future responders/non-responders to a-tDCS treatments of PSF. Pearson's correlations will be calculated between baseline measures of inflammation and FSS scores to determine a possible role of current state inflammation on PSF severity. Correlations between the change in FSS scores and inflammation, pre- and post-a-tDCS, will be calculated to provide preliminary evidence of a possible mechanism of reduced inflammation and improved PSF.

Potential Problems / Solutions

Some groups have reported a 50% response rate to tDCS. Due to our small sample, non-responders may reduce our statistical power. A post-hoc response analysis, defined as a change greater than the minimally clinically important difference of 0.45 (Nordin et al. 2016), will be performed to power future studies. Placing the ¹H-MRS voxel within the basal ganglia is a logical starting place based on the published literature. However, it is possible that inflammatory markers outside this region are as influential or more so than basal ganglia measures. Future work may be required to determine which brain regions are best to assess with ¹H-MRS. Another limitation is that only a-tDCS is being tested. Cathodal tDCS (c-tDCS) has been reported to have similar long-term effects on gene expression and protein synthesis. The benefits of tDCS on fatigue, to date, have mostly investigated a-tDCS although future investigations need to determine if c-tDCS may be a viable treatment option. Another area that will need to be addressed in future studies is if our post-intervention measurements of metabolite changes reflect the last episode of treatment or if they are indicative of long-term changes in response to tDCS. Future studies will also need to assess the optimal intervention length and follow-up periods.

Biostatistical Justification

This pilot work is based on a similar study investigating a-tDCS' effects on post-stroke fatigue (De Doncker et al. 2021). The FSS is the primary measure of fatigue severity and the minimally clinically important difference (MCID) was reported to be 0.45 (Nordin et al. 2016), with changes greater than this resulting in reported improvements in QOL. To detect this level of change with 80% power and an alpha = 0.05 between two groups using a within-between-subjects interaction ANOVA a minimum sample of 8 individuals in each group is required. We will enroll 24 participants (12 a-tDCS, 12 sham) to account for any drop-out, loss to follow-up, or complications during data collection. We have projected to perform recruitment and data collection activities over nine months.

REFERENCES

Altas, E. U., Askin, A., Besiroglu, L., & Tosun, A. (2019). Is high-frequency repetitive transcranial magnetic stimulation of the left primary motor cortex superior to the stimulation of the left dorsolateral prefrontal cortex in fibromyalgia syndrome? *Somatosens Mot Res*, 36(1), 56-62.

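### The 36-hour withdrawal rule leaves no stated follow-up FSS for those it removes, so the primary comparison probably loses randomised participants

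*Combined protocol and SAP*

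**What the plan says.** - **Study Design and a-tDCS Treatment.** Participants are randomly assigned to sham or active stimulation. Treatment visits are on consecutive days (Days 2-6), at most 36 hours apart, and then: "If more than 36 hours elapses the participant will be withdrawn from the study". The word used is study, not stimulation.
- **Same section.** The primary outcome compares the FSS at Visit 1 with the FSS at Follow-up 1, one week after stimulation. "Follow-up assessments of state and trait fatigue will be performed via phone".
- **Figure 2 legend.** "Three additional followup phone-calls to assess fatigue will be performed 1, 2, and 4 weeks post the participants' last tDCS treatment". The legend does not say whether this includes people withdrawn under the 36-hour rule.
- **Statistical Analysis, Aim 1.** The test uses a between-subjects GROUP factor and a "within-subjects factor of TIMEPOINT (pre, post), mixed model ANOVA will be used to test this hypothesis". No analysis set and no method for missing values is given.
- **Biostatistical Justification.** The MCID is 0.45, and 24 people (12 per arm) are enrolled to allow for losses.
- **DSMP Administration.** The investigator will look through the database for missing data. What follows from that is not stated.
- **Documentation and Reporting.** Continued follow-up is provided for adverse events, not for the FSS.

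**The concern.** A treatment visit presupposes an assigned arm, so the rule is an exclusion after randomisation. With visits on consecutive days, one missed day would normally exceed 36 hours. Everyone enrolled has clinically significant, persistent fatigue, so a missed visit could be related to the outcome itself; that is an inference, not something the documents report.

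The GROUP by TIMEPOINT contrast needs a value before and a value after. If those withdrawn have no Follow-up 1 FSS, the contrast rests on people who kept to the schedule, and randomisation no longer guarantees that the two arms are alike. Nor could anyone check afterwards whether the loss mattered, because the values needed would not exist. With 12 per arm, each person removed is 1/12, or 8%, of an arm.

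**Working it through.** **The plan's own figures.** The Biostatistical Justification states that "a minimum sample of 8 individuals in each group is required". It gives no SD and no pre/post correlation, so this cannot be reproduced from stated inputs. Back-solving with 0.45 read as FSS points, 80% power and a two-sided 5% test on change scores, 8 per group implies an SD of change of about 0.30. The loss allowance is 24 − 16 = 8 people, or 8/24 = 33%. It keeps the numbers up, but says nothing about whether those who remain are comparable between arms.

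**When a shift arises.** Let p be the share of an arm withdrawn, and d the mean FSS change of those withdrawn minus that of the others in the arm (A active, S sham). Then

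shift in group difference = pA × dA − pS × dS.

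It is zero when p and d are the same in both arms. Equal withdrawal rates alone do not make it zero.

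**Illustration.** Only the 12 per arm and the MCID of 0.45 come from the protocol. The withdrawal counts and d = 0.5 are assumed.

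| Withdrawn, by arm | d | Shift | Share of 0.45 |
|---|---|---|---|
| 1 v 0 | 0.5 | 1/12 × 0.5 = 0.04 | 9% |
| 2 v 0 | 0.5 | 2/12 × 0.5 = 0.08 | 19% |
| 2 v 2 | 0.5 in both arms | 0.08 − 0.08 = 0 | 0% |
| 2 v 2 | 0.5 in one arm, 0 in the other | 0.08 − 0 = 0.08 | 19% |

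Halving d halves each shift. Swapping the arms reverses its sign.

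**Against sampling error.** SE = SD × √(1/n1 + 1/n2).

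- 2 v 0 leaves 10 v 12: SE = 0.428 × SD, which is 0.21 at an assumed SD of change of 0.5 and 0.43 at 1.0. A shift of 0.083 is then 0.39 or 0.19 SE. At the back-solved SD of 0.30 it is 0.083/0.128 = 0.65 SE.
- 1 v 0 leaves 11 v 12: SE = 0.417 × SD. A shift of 0.042 is 0.20 SE at SD 0.5 and 0.10 SE at SD 1.0.

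**Selection or dilution?** Suppose the true effect is 0.45 and 2 of 12 active participants stop early and gain nothing. The effect over all 12 is 0.45 × 10/12 = 0.375, a shift of 0.075. The 2 v 0 figure of 0.08 could therefore be almost wholly the effect of receiving less treatment, with no selection.

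**Chance imbalance.** If two of the 24 are withdrawn for reasons unrelated to arm, both come from the same arm with probability 2 × C(12,2)/C(24,2) = 2 × 66/276 = 48%. An uneven split is not in itself evidence of an arm-related cause.

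**The case against.** The strongest reply has four parts.

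1. **The exclusion is read from silence.** A reader might infer that the plan declares these people uncalled and unanalysed. It does not say so, and the Figure 2 legend times the calls from the last treatment, a date that exists for anyone treated at least once. This stands as a limit on the claim. Withdrawal from the study is still most naturally read as ending study contact, and nothing states otherwise.

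2. **The full regimen is the question.** Aim 1 reads "Five days of a-tDCS applied to the lower extremity motor cortex will result in a reduction of PSF severity in individuals with chronic stroke", and the Summary of the Protocol describes five sessions. Studying people who complete a short regimen is a recognisable choice in a pilot, and it deserves a place in the report. But a comparison of rule-compliant participants is no longer the randomised one.

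3. **No arm-related cause is shown.** A reader might infer that the estimate is pushed in a known direction, more so because the trial is single-blind and the investigator delivers the treatment. The documents do not support that. The trigger is a visit gap, the listed common side effects are minor (Research Procedures and Potential Risks), and the group reports over 100 sessions without adverse events (Protections Against Risk). If withdrawal and its link to outcome are the same in both arms, the expected shift is zero. The four spare places per arm are an allowance, not a forecast of losses.

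4. **The pilot only informs later work.** The plan says "We will also calculate measures of effect size to power future studies", and a reader might infer that the next trial would be wrongly sized. That would rest wholly on assumed inputs. Sampling error in so small a trial is larger than the shifts shown, and Data Management and Analysis promises 95% confidence intervals. Intervals convey imprecision, though not bias.

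It is also fair to say that this rule is one route into a wider gap: no analysis set covers drop-out or loss to follow-up either.

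**Conclusion.** The point holds as a gap in outcome collection and in the definition of the analysis set. The wording of the rule and its timing after assignment are certain. That those withdrawn lack a Follow-up 1 FSS is the most natural reading, not a stated fact. Over-enrolment does not answer it.

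Its frequency, size and direction are unknown. The 0.04 and 0.08 points are illustrations that assume 1 or 2 withdrawals in one arm only and a 0.5-point difference in FSS change. They are below sampling error at each SD tried (0.30, 0.5 and 1.0), and they cannot separate selection from less treatment received. They do not show that the result will be biased. The plan should still be changed, because the change is cheap and an FSS that was never collected is unlikely to be recovered later.

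**What to change.** Leave the 36-hour limit and its consequence for stimulation as they are. Add text on outcome collection and analysis only:

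- Participants to whom the rule applies, if they continue to agree, still receive the Follow-up 1, 2 and 3 FSS calls, timed from their last tDCS treatment.
- The primary GROUP by TIMEPOINT analysis includes all randomised participants with a baseline and a Follow-up 1 FSS, in their assigned group.
- The rule-compliant set is reported as a sensitivity analysis of the full five-day regimen.
- The number to whom the rule applied and the number missing Follow-up 1 are reported by arm.

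**Cost.** A few sentences, and at most three calls per affected participant, within the 24 × 3 = 72 already planned. The rule is triggered 36 hours after a session and Follow-up 1 falls seven days after the last one, so the call date is still ahead. Follow-up calls are already a payment milestone (Retention).

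**Downside.** The estimate is diluted if early stoppers gain nothing: 0.45 becomes 0.45 × 11/12 = 0.41 with one of 12 active participants stopping, and 0.375 with two. Under an assumed 5% chance of breaking the rule at each of four gaps, 1 − 0.95^4 = 18.5% stop in each arm. Signal-to-SE relative to full completion is then 0.81 with everyone included, against √0.815 = 0.90 in the rule-compliant set. The gain is comparability of the arms, not power. Participants who still miss Follow-up 1 remain excluded, so the problem is reduced, not removed, and the report should say so.
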